### 14.12 Visit 12: 52 weeks after starting extended YF476 dosing

The investigator will repeat the procedures from Visit 8, do a gastroscopy and take gastric biopsies, but will not issue a new diary card or a new container of YF476. After collecting the fasting blood sample and doing the gastroscopy, the investigator will give the patient their dose of YF476, wait 1 h, and then collect blood for assay of peak YF476 concentration.

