#### 6.3 Flowchart for extended treatment

1. Patients fast overnight before the visit and bring their container of YF476 with them.

- 2. The investigator will carry out the following procedures: Medical examination, 12-lead ECG, vital signs, safety tests of blood and urine, fasting serum gastrin, plasma CgA and serum for storage, plasma YF476 (before and 1 hour after dosing), and pregnancy test (women of child-bearing potential only). The investigator will collect and check diary card, collect and check YF476 container for compliance, and ask the patient about adverse events and concomitant medication.
- 3. The investigator will issue YF476 capsules and diary card.
- 4. Patients must fast from food and fluid for at least 6 hours before gastroscopy. They will take YF476 only after the gastroscopy.
- 5. If the investigator thinks that a new baseline gastroscopy is needed, the patient will be informed of this before visit 8, and must fast from food and fluid for at least 6 hours before gastroscopy.
- 6. Blood sampling to include safety tests, fasting serum gastrin and plasma CgA, if the investigator thinks it is necessary.

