#### **Extended treatment**

Some patients will be eligible for extended treatment with YF476, as described below. To be eligible for further treatment, the patient must have benefitted from 12 weeks' treatment, and have tolerated YF476 well, and must give fully informed written consent.

**Visit 8** will be to inform the patient about the extended dosing period and prescribe YF476 capsules. If the investigator thinks that a new baseline gastroscopy and blood sampling (for safety, gastrin and CgA) is necessary, this will be carried out.

**Visit 9** will be 12 weeks after starting extended treatment with YF476, to assess tolerability, safety and blood levels of gastrin, CgA and YF476.

**Visit 10** will be 24 weeks after starting extended treatment with YF476, to assess tolerability and safety, to repeat the gastroscopy and gastric biopsies, and to take blood samples to assess blood levels of gastrin, CgA and YF476.

**Visit 11** will be 36 weeks after starting extended treatment with YF476, to assess tolerability, safety and blood levels of gastrin, CgA and YF476.

**Visit 12** will be 52 weeks after starting extended treatment with YF476, to assess tolerability and safety, to repeat the gastroscopy and gastric biopsies, and to take blood samples to assess levels of gastrin, CgA and YF476.

A formal follow-up visit will be omitted, as the patients are closely followed by the investigator as part of their standard healthcare.

The end of the trial will be the last visit by the last subject.

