### 14.7 Visit 7: 12 weeks after stopping YF476

Visit 7 will be a follow-up visit for patients who respond to YF476. The gastroscopy and blood sampling for fasting gastrin and CgA will be repeated.

Some patients will be eligible for extended treatment with YF476, as described below. To be eligible for further treatment, the patient must have benefitted from 12 weeks' treatment, and have tolerated YF476 well, and must give fully informed written consent.

### 14.8 Visit 8

The investigator will:

• tell the patient about the extended dosing period and ask him or her to read the information about the extended dosing and sign the consent form;

- do a gastroscopy and take gastric biopsies if the investigator thinks that a new baseline gastroscopy is necessary. If this is the case, the patient will have been told in advance and will be asked to fast for ≥6 h before the visit;
- collect blood for safety tests and for assay of fasting levels of gastrin and CgA if the investigator thinks that new baseline values are necessary;
- give the patient a container of YF476 capsules (25 mg) and instructions on how many to take daily with breakfast, starting the following day; and
- give the patient a diary card, to record YF476 doses, any adverse events, and any concomitant medication.

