# 14.10 Visit 10: 24 weeks after starting extended YF476 dosing

The investigator will repeat the procedures from visit 9 and:

- do a gastroscopy and take gastric biopsies, and proceed as follows:
  - if on visual inspection the gastric carcinoids have regressed completely: stop YF476, omit Visits 11 and 12, providing all safety assessments prove satisfactory; or
  - if on visual inspection gastric carcinoids are still present: continue treatment with YF476 once daily.

• after collecting the fasting blood sample and doing the gastroscopy, give the patient their dose of YF476, wait 1 h, and then collect blood for assay of peak YF476 concentration; and instruct the patient about Visit 11.

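### Section 14.12 sends Visit 12 (week 52) back to the Visit 8 consent list, contradicting the full safety and biomarker check scheduled in 6.3, 2.6 and 9

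*Protocol*

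**What the plan says.** Section 14.12 defines Visit 12 mainly by reference: "The investigator will repeat the procedures from Visit 8, do a gastroscopy and take gastric biopsies, but will not issue a new diary card". It issues no further capsules and adds a YF476 blood sample 1 h after dosing. It also contains the clause "After collecting the fasting blood sample and doing the gastroscopy, the investigator will give the patient their dose of YF476".

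Visit 8, described in Section 14.8, opens the extension. The investigator is to "tell the patient about the extended dosing period and ask him or her to read the information about the extended dosing" and obtain consent. The other steps are conditional or concern supply: "do a gastroscopy and take gastric biopsies if the investigator thinks that a new baseline gastroscopy is necessary"; "collect blood for safety tests and for assay of fasting levels of gastrin and CgA if the investigator thinks that new baseline values are necessary"; then capsules and a diary card are handed out.

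Three other places describe Visit 12 differently. The 6.3 flowchart labels it a safety and efficacy check and attaches note 2, which begins "Medical examination, 12-lead ECG, vital signs, safety tests of blood and urine, fasting serum gastrin, plasma CgA and serum for storage" and goes on to plasma YF476 before and 1 h after dosing, a pregnancy test, and diary and container checks. Sections 2.6 and 9 both say the visit assesses tolerability and safety and takes blood for gastrin, CgA and YF476, with no discretion.

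The matching instruction for week 24, in Section 14.10, is "The investigator will repeat the procedures from visit 9". On what follows Visit 12, Section 9 says "A formal follow-up visit will be omitted".

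**The concern.** Section 14 is the step-by-step text from which a site runs a visit. A reader who follows 14.12 to Visit 8 finds a consent procedure and optional baseline tests where the flowchart has a compulsory end-of-treatment check.

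Four things are at stake at week 52:

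- **QTc and liver enzymes.** Section 10.4 bases two of its four extension criteria on ALT/AST and QTc. It also counts subjects across the trial, since two or more meeting a criterion stops dosing in all. A week-52 result could therefore bear on patients still being treated.
- **Gastrin and CgA.** The effect on biomarkers such as CgA is a secondary objective. If the final sample were taken only when the investigator thought it necessary, the patients with a week-52 value could be a selected subset.
- **Trough YF476.** Section 18.1 uses plasma YF476 concentrations to look for a relationship with CgA and gastrin.
- **Long-term safety.** The longest dosing among the completed studies listed in 7.8.5 is 6 weeks, so week-52 safety data would be new information.

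With no formal follow-up visit afterwards, an item missed at Visit 12 is not picked up at a later scheduled trial visit.

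**Working it through.** No figure in the plan is involved. The check sets the visit lists side by side.

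| Assessment | 14.8 (Visit 8) | Added by 14.12 itself | 14.9 (Visit 9, repeated at Visit 10) | 6.3 chart and note 2 (Visit 12) |
|---|---|---|---|---|
| 12-lead ECG | no | no | yes | yes |
| Blood pressure, heart rate | no | no | yes | yes |
| Safety bloods | optional | not named | yes | yes |
| Urine safety tests | no | no | yes | yes |
| Pregnancy test (where applicable) | no | no | yes | yes |
| Gastrin and CgA | optional | fasting sample presupposed, assays not named | yes | yes |
| Trough YF476 | no | not named | yes | yes |
| YF476 1 h after dosing | no | yes | yes | yes |
| Stored serum | no | no | yes | yes |
| Gastroscopy | optional | yes | no (added by 14.10) | yes |
| Diary and container check | no | no | yes | yes |
| Medical examination | no | no | no | yes |

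Reading across:

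1. Visit 8 plus the additions in 14.12 gives gastroscopy, biopsies and the post-dose YF476 sample as firm requirements. ECG, vital signs, urine and pregnancy tests, trough YF476 and stored serum are not listed. Safety bloods, gastrin and CgA carry over as optional.
2. The diary and container check is missing from both lists, but Section 11.5 requires it at every clinic visit. It therefore applies at Visit 12 whatever 14.12 refers to. Section 14.14 likewise has the investigator ask about adverse events at each visit.
3. The fasting-sample clause in 14.12 means that some pre-dose blood is drawn. It does not say which assays are run.
4. Replacing Visit 8 with Visit 9 in 14.12 would restore every item except the last row. Note 2 of 6.3 lists a medical examination for Visits 9 to 12, but 14.9 and 14.11 do not list one, and 14.10 and 14.12 do not add one. That is a second, smaller mismatch.
5. The context points to a slip. Taken literally, 14.12 would have the patient consent to extended dosing on the day it ends. Its mention of withholding a new diary card and container fits Visits 9 and 11, where replacements are issued.

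**The case against.** The strongest reply is that the assessments are scheduled. The 6.3 flowchart, Section 2.6 and Section 9 agree, and a single cross-reference is out of step. Because the literal reading is absurd (consent to a treatment period that is ending), most investigators would turn to the flowchart and do the full check. Sections 11.5 and 14.14 independently secure the compliance check and the adverse-event enquiry. Few patients are affected: the trial has up to 10, only some enter the extension, and under 14.10 those with complete regression at Visit 10 omit Visit 12.

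Most of this stands, and it limits the point to an internal contradiction. It does not remove the point, because the wrong reference sits in the operative visit text and nothing in the protocol says that 6.3 prevails over Section 14.

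Two stronger readings should be resisted.

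- A reader might infer that the protocol provides no week-52 safety or biomarker data. It does provide them, in three places.
- A reader might note that Visit 11 is at week 36 and infer that the last 52 − 36 = 16 weeks of dosing lose their monitoring. Even with 14.12 corrected, no visit is scheduled between weeks 36 and 52. What is in doubt is the content of one time point. Moreover, Visit 12 gives the last dose and issues no capsules, so withdrawing that individual patient under 10.4 is largely moot by then.

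**Conclusion.** The point holds as a contradiction within the protocol. Section 14.12 refers Visit 12 to a visit list that does not match 6.3 note 2 or Sections 2.6 and 9, and the parallel instruction in 14.10 shows the pattern used elsewhere.

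Its reach is one visit, in those of at most 10 patients who enter the extension and reach week 52. For them, a site that works from 14.12 alone could miss the ECG, vital signs, urine and pregnancy tests, trough YF476 and stored serum, and could treat safety bloods, gastrin and CgA as discretionary. Whether any data would be lost depends on which section the site follows, which the document does not settle. The conclusion does not extend to the diary and container check, the adverse-event enquiry, gastroscopy, biopsies or the post-dose YF476 sample, all of which remain required.

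It is worth correcting because this is the last scheduled assessment and the correction costs almost nothing.

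**What to change.** Reconcile 14.12 with 6.3 note 2 and Sections 2.6 and 9, so that Visit 12 carries the compulsory assessment set already scheduled there, as at Visit 10, in place of the reference to Visit 8. Name the assays to be run on the fasting sample, including trough YF476. Separately, align the medical-examination entry between 6.3 note 2 and Sections 14.9 to 14.12, since changing the visit number alone would leave that mismatch.

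The cost is one corrected cross-reference and one aligned entry. Relative to the flowchart, no procedure, visit or blood draw is added.

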### 14.13 Flexibility of study days

It may not always be possible to carry out the gastroscopies on scheduled days. Therefore, if necessary, gastroscopy visits may be delayed or brought forward by up to 3 days. Other visits may be made up to 2 days before or after the scheduled day. Patients will be given sufficient YF476 to cover such delays.

## 14.14 Methods

*Collection of samples for laboratory safety tests:* Blood will be taken for haematology and biochemistry according to local procedures. Urine will be collected in 60 mL Universal containers. Sample handling materials will be provided by the investigator.

*Processing of blood samples for laboratory safety tests:* Blood samples for biochemistry and haematology will be processed according to local procedures and sent to Joint Pathology Services, Duncan Building, Royal Liverpool University Hospital.

*Laboratory safety tests:* The Royal Liverpool University Hospital Laboratory will do safety tests on blood samples according to local procedures.

The investigator will do safety tests on urine samples according to local procedures. If results of the tests are abnormal, the laboratory will do microscopy.

*Pregnancy test*: urine will be tested using a commercially available test kit.

Collection and processing of blood samples for serum gastrin and stored serum: Venous blood for serum gastrin assay and stored serum  $(2 \times 2.5 \text{ mL})$  will be collected into polypropylene tubes and will be allowed to clot at room temperature for at least 20 min. After clotting, the tubes will be centrifuged at about 1500 G for 10 min at 4°C, and the serum transferred to smaller tubes in equal aliquots then stored at -20°C before shipment to the HMR Analytical Laboratory, [name]. Serum samples for gastrin assay and storage will be shipped once the patient has completed the study. All sample handling materials will be provided by the HMR Analytical Laboratory.

### Collection and processing of plasma for CgA assays:

4 mL venous blood will be collected into an EDTA tube and centrifuged at about 1500 G for 10 minutes at 4°C. The plasma will be transferred into 2 equal aliquots in polypropylene tubes, and stored at –70°C, before shipment to the HMR Analytical Laboratory, [name]. Plasma samples for CgA assay will be shipped once the patient has completed the study. All sample handling materials will be provided by the HMR Analytical Laboratory.

*Gastrin assay and plasma CgA assay:* Serum gastrin and plasma CgA will be measured by the HMR Analytical Laboratory using commercially available enzyme linked immunoassays (ELISA).

*Processing of blood samples for pharmacokinetic analysis:* YF476 is light-sensitive, so blood samples (4 mL) will be taken into foil-wrapped or amber lithium heparin tubes, and immediately placed on ice. Samples will be centrifuged at about 1500 G for 10 minutes at 4°C. Plasma will be transferred to foil-wrapped or amber polypropylene storage tubes. Plasma samples will be stored at –20°C within 90

minutes after collection, and stored in darkness until dispatch. Samples will be sent to Analytical Services, St George's Hospital, for analysis of YF476.

*Stored serum:* serum will be stored by the HMR Analytical Laboratory for assay of trial-related markers only, which will be decided upon at a later date.

*Gastroscopy:* a gastroenterologist who is experienced and trained in the procedure will do the gastroscopies and biopsies. Subjects must have fasted from food and fluids for at least 6 hours before the procedure. Before the procedure, patients will choose whether they want to be sedated with intravenous midazolam, or have their throat sprayed with a local anaesthetic. After gastroscopy, patients will rest until they are fully recovered from the procedure. They may eat 30 min after the procedure.

During the procedure, the distribution, number and size of any gastric carcinoids will be assessed visually, and the tumors will be photographed. A pair of standard biopsy forceps will be used as an internal standard for size correction between images. Biopsies will be taken of the antrum, corpus and carcinoids for histology assessment and assessment of ECL cell markers and biomarkers (such as CgA).

*Histologic evaluation:* [name], Liverpool, will do the histology. Histologic evaluation will include the following:

- haematoxylin and eosin (H&E) staining;
- immunostaining for neuroendocrine markers including CgA and synaptophysin; and
- histologic grading.

Samples will initially be read and reported through the standard pathology reporting system. At the termination of the study, all samples will be read by a single expert pathologist who is blinded to identifying patient information and to treatment status (pre-treatment, during-treatment or post-treatment).

*ECL cell and biomarker evaluation:* The Physiology Laboratory, Liverpool, will do the ECL-cell markers. [name], Liverpool, will do the biomarkers.

**Blood pressure and heart rate** will be measured using an automatic method. At screening, measurements will be made with subjects in the supine position; subjects will remain supine for at least 3 min before vital signs are measured.

**Standard 12-lead ECGs** will be recorded using an electrocardiograph. Each recording will be printed on a single A4 page at paper speed 25 mm/sec and calibrated to 1 cm/mV, or to 0.5 cm/mV if the amplitude of the QRS complex requires that. Recordings will be made with subjects in a supine position; subjects will remain supine for at least 10 min before the ECG is recorded.

*Medical examinations* will be done by a physician. The following sites will be examined: head, neck, ears, nose, throat, eyes, chest, lungs, heart, abdomen, skin, and

lymph nodes; and the following systems will be assessed: musculoskeletal and neurological.

*H. pylori test:* The test will be done, according to local standard operating procedures, only if the patient's *H. pylori* status is unknown.

*Diary card:* Patients will record daily in the diary card: adverse events, YF476 treatment, and any other medicines taken.

*Adverse Events:* Adverse events will be recorded in the patient's diary card. The investigator will also question patients about adverse events at each visit.

# 14.15 Total volume of blood removed

The total volume of blood taken from each subject in the trial will be up to 275 mL (including 'overage' for repeat safety tests if necessary).

[figure not shown]
# 14.16 Precautions

As YF476 is light-sensitive, special care is needed to prevent its degradation during the handling of blood and plasma samples. Containers must be lightproof, or be foil-wrapped and amber tinted if they are translucent. If that is not feasible, materials must be handled in darkened rooms, with light of a wavelength >450 nm and an intensity below 20 Lux.

# 15 Trial materials

# 15.1 Active pharmaceutical ingredient (API): YF476

Structural formula:

Chemical formula:	(R)-1-[2,3-dihydro-2-oxo-1-pivaloylmethyl-5- (2-pyridyl)-1 H -1,4-benzodiazepin-3-yl]-3-(3- methylaminophenyl)urea
Molecular formula:	$C_{28}H_{30}N_6O_3$
Molecular weight:	498.58
Description:	white to off-white / yellow crystals or crystalline powder
Purity:	$\geq 99.0\%$
Melting point:	about 230°C (with decomposition)
Optical rotation:	$[\alpha]D^{20} = +120 - 128^{\circ}C (c = 0.5\% \text{ in acetone})$
Acid dissociation constant (pKa):	2.53, 4.59
Hygroscopicity:	<0.3% at room temperature, and 93% relative humidity (7 days)
Stability:	Chemically stable for at least 9.5 years at room temperature, protected from light.

#### 15.3 Final formulation

The co-formulation of spray-dried YF476 and HPMC will be blended with starch, and placed into hard gelatine capsules by HMR Pharmacy. Each capsule will contain 25 mg YF476. The sponsor will provide a certificate of analysis for the test product, and any other documents and data required by the Qualified Person to release batches of investigational medicinal product (IMP).

## 15.3.1 Packaging and labelling

The trial medication will be packaged and labelled for each subject by the HMR Pharmacy, in accordance with The Rules Governing Medicinal Products in the European Union, Volume 4: Good Manufacturing Practice (GMP), and HMR's Manufacturing Authorisation for Investigational Medicinal Products [MIA(IMP)]. The IMP labels will include all the information required by Revision 1 of Annex 13 to GMP, as follows:

- name of the sponsor;
- pharmaceutical dosage form, route of administration, quantity of dose units, and name and strength of the medication;
- batch number and/or code number to identify contents and packaging operation;
- trial subject identification number;
- name of investigator;
- directions for use;
- 'clinical trial use only';
- trial reference code, allowing identification of the trial site and investigator;
- storage conditions;
- period of use (use-by date, expiry date, or re-test date, as applicable) in month/year format; and
- 'keep out of reach of children'.

### 15.3.2 Storage and accountability of IMP

The HMR Pharmacy will despatch the IMP to the investigator after ethical and regulatory approval of the trial have been obtained. The investigator will record and acknowledge in writing the receipt of all supplies of IMP.

The IMP will be stored securely at 2–8 °C, accessible only to those individuals authorised by the investigator to dispense the IMP.

An inventory will be maintained, which will include the description and quantity of IMP received. A record will be kept of the IMP that is dispensed, to which subject, and the date and time of administration.

At the end of the trial, all unused IMP supplies will be returned to the sponsor.

# 16 Adverse events

### 16.1 Definitions of adverse events

#### Adverse event

Any untoward medical occurrence in a patient or clinical trial subject administered a medicinal product and which does not necessarily have a causal relationship with that treatment.

### Adverse drug reaction

All untoward and unintended responses to an investigational medicinal product related to any dose administered.

Note that, according to the ICH Guideline for Good Clinical Practice (ICH GCP), a causal relationship between the medicinal product and the adverse event is at least a reasonable possibility, ie a relationship cannot be ruled out.

#### Unexpected adverse drug reaction

An adverse reaction, the nature or severity of which is not consistent with the applicable product information (eg Investigator's Brochure for an unauthorised investigational product, or summary of product characteristics for an authorised product).

